6.2. Safety Endpoints

- DLT is the primary endpoint of the dose escalation component of the study. The occurrence of DLTs observed in the dosing cohort is used to estimate the MTD. Adverse Events constituting DLTs will be listed per dose level.
- Adverse Events (AEs): Treatment Emergent Adverse Events, those with initial onset or increasing in severity after the first dose of study medication.

- AEs will be graded by the investigator according to CTCAE version 4.03 and coded using the Medical Dictionary for Regulatory Activities (MedDRA). The number and percentage of subjects who experienced any AE, SAE, treatment related AE, and treatment related SAE will be summarized according to worst toxicity grades. The summaries will present AEs both on the entire study period and by cycle.
- Laboratory abnormalities.
- Vital signs.
- ECGs.
- Cytokine Release Syndrome: The severity of cytokine release syndrome (CRS) will be assessed according to the modified grading described by Lee et al 2019 for SC cohorts and Lee et al 2014 for IV cohorts. (Appendix 5 of the protocol).

6.2.1. DLT Evaluability Criteria

For the purpose of dose escalation, the DLT observation period will be up to the end of Cycle 1 in each patient. For those patients receiving a priming dose, Cycle 0 and Cycle 1 would be included in the DLT observation period. DLT evaluable patients will include patients that have experienced a DLT in the DLT observation period or. DLT evaluable patients will also include those who received all of their planned doses of PF-06863135 in the initial DLT observation period if Q2W dosing is being evaluated or at least all but one of their planned doses of PF-0686135 if Q1W dosing is being evaluated, provided a dose was not missed due to toxicity attributed to study drug. Safety information from any patients that do not meet DLT evaluable criteria could still be considered for overall dose escalation decisions although they would not factor into mTPI decision rules.

The following criteria will be used to assess adequate dosing for DLT evaluability:

- Part 1 (no priming): At least 1 dose of the PF-06863135.
- Part 1.1 Q1W: 75% of the planned PF-06863135 dose regimen in cycle 1, i.e. 28 days from C1D1. The total planned dose as per protocol = (maintenance dose * 4).
 - Dose administered dose will be the sum of Calculated Dose
Administered=Volume of PF-06863135 administered * Concentration of PF-06863135 formulation /body weight for the first 28 days.
- Part 1.1 Q2W: 75% of the planned dose regimen in cycle 1, i.e. 28 days from C1D1. The total planned dose as per protocol = (maintenance dose * 2).
 - Dose administered dose will be the sum of Calculated Dose
Administered=Volume of PF-06863135 administered * Concentration of PF-06863135 formulation/ body weight for the first 28 days.

- Part 1C and 1D: [(75% of the planned PF-06863135 dose) AND (75% of the planned combination drug dose)] in cycle 1, i.e., 28 days from C1D1.
 - The total planned PF-06863135 dose = (maintenance dose * 4).
 - The total planned Lenalidomide dose = (planned Lenalidomide dose in mg * 21).
 - The total planned Pom dose = (planned Pomalidomide dose in mg * 21).
 - Dose administered should be the sum of calculated actual dose administered for the first 28 days.
- Part 1E: [(75% of the planned PF-06863135 dose) AND (75% of the planned Dexamethasone dose)] in cycle 1, i.e., 28 days from C1D1.
 - The total planned PF-06863135 dose = (maintenance dose * 4).
 - The total planned Dexamethasone dose = (planned Dexamethasone dose in mg * 4). *Dexamethasone will be administered at a dose of 40 mg weekly. For subjects older than 75 years or underweight (body mass index [BMI] <18.5), the dexamethasone dose may be administered at a dose of 20 mg weekly. Dexamethasone may be reduced, if necessary, according to Table 10 in the protocol.*

Relative dose intensity at each cycle will be calculated as follows:

- Part 1 (no priming): Cycle length is determined as entered by the site.
 - Dose administered will be the sum of “Calculated Dose Administered” for the cycle.
 - The total planned dose will be the (assigned dose of PF-06863135 *3)
 - If patient discontinues before end of the cycle, the planned dose for the will be based on dosing for number of days on the last cycle based on the dosing page. For example, if patient discontinues after CXD2, the planned dose will be (assigned dose of PF-06863135 *1).
- Part 1.1 Q1W and Part 2A: Cycle length is determined as entered by the site.
 - The total planned dose = (maintenance dose of PF-06863135 * 4).
 - Dose administered will be the sum of “Calculated Dose Administered” for the cycle.
 - If patient discontinues before end of the cycle, the planned dose for the will be based on dosing for number of days on the last cycle based on the dosing page.
- Part 1.1 Q2W: Cycle length is determined as entered by the site.
 - The total planned dose = (maintenance dose of PF-06863135 * 2).
 - Dose administered will be the sum of “Calculated Dose Administered” for the cycle.
 - If patient discontinues before end of the cycle, the planned dose for the will be based on dosing for number of days on the last cycle based on the dosing page.

- Part 1C and 1D: Cycle length is determined as entered by the site.
 - The total planned PF-06863135 dose = (maintenance dose * 4).
 - The total planned Lenalidomide dose = (assigned dose of Lenalidomide in mg * 21).
 - The total planned Pomalidomide dose = (assigned Pomalidomide dose of mg * 21).
 - Dose administered should be the sum of “calculated actual dose” for the cycle.
 - If patient discontinues before end of the cycle, the planned dose for the lenalidomide/pomalidomide will be based on daily dosing for min(number of days on the cycle, 21) as entered in the dosing page .
- Part 1E: Cycle length is determined as entered by the site.
 - The total planned PF-06863135 dose = (maintenance dose * 4).
 - The total planned Dexamethasone dose = (assigned dose of Dexamethasone * 4).
 - Dose administered should be the sum of “calculated actual dose” for the cycle.
 - If patient discontinues before end of the cycle, the planned dose for the will be based on dosing for number of days on the last cycle based on the dosing page.

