1.2.3.1. Safety

The safety, efficacy, and PK of elranatamab were initially evaluated in Phase 1 study (C1071001) as monotherapy (IV and SC) or in combination with lenalidomide or pomalidomide.

As of the 22 June 2022 data cutoff date, 101 participants have been enrolled in the study as follows: 23 in Part 1 IV dose escalation, 30 in Part 1 SC dose escalation, 20 in Part 1.1 SC priming dose cohorts, 15 in Part 2A: SC dose dose expansion, 4 in Part 1C: elranatamab + lenalidomide and 9 in Part 1D: elranatamab + pomalidomide. In Part 1.1, to mitigate the risk of CRS and ICANS, participants received a priming dose of 600 µg/kg elranatamab (equivalent to 44 mg) on Day 1 prior to the first full dose of 1000 µg/kg (equivalent to 76 mg) on Day 8. In Part 2A, in addition to the priming dose of elranatamab, participants received pre-medication with dexamethasone, acetaminophen and diphenhydramine prior to the first 2 doses, priming dose and first full dose respectively.

Based on the data from this study, 76 mg QW administered SC was selected as the RP2D of elranatamab for future studies. This section will focus on safety data from participants who received elranatamab monotherapy at the full 1000 µg/kg or 76 mg [QW or Q2W] dosing regimen (N=41) regardless of priming dose or premedication.

In the 41 participants who received elranatamab monotherapy at the full 1000 µg/kg or 76 mg [QW or Q2W] dosing regimen, the most common all causality TEAEs (frequency $\geq 20\%$) were CRS (87.8%), neutropenia (78.0%), anemia (63.4%), ISR (56.1%), thrombocytopenia and fatigue (each 48.8%), diarrhea, hypophosphatemia and lymphopenia (each 39.0%), decreased appetite and dry skin (each 36.6%), back pain (34.1%), nausea and hypomagnesaemia (each 31.7%), AST increased and leukopenia (each 26.8%), ALT increased, fall, hypokalemia, pyrexia, vomiting, pain in extremity and weight decreased (each 24.4%), arthralgia, cough, dyspnoea, headache and pneumonia (each 22.0%).

For additional information, refer to the single reference safety document (SRSD), which for this study is the Investigator's Brochure.

PF-06863135
C1071001
Final Protocol Amendment 9, 28 March 2023

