3.2. Dose Limiting Toxicity (DLT) Definition

Monitoring for DLTs will occur during Part 1. Severity of adverse events (AEs) will be graded according to National Cancer Institute Common Terminology Criteria for Adverse Events (CTCAE) version 4.03. The severity of cytokine release syndrome (CRS) will be assessed according to the grading described by Lee et al. (2014 and 2019,^{2,3} See [Appendix 5](#)). For the purpose of dose escalation, the DLT observation period will be up to the end of Cycle 1 in each patient. For those patients receiving a priming dose, Cycle 0 and Cycle 1 would be included in the DLT observation period. DLT evaluable patients will include patients that have experienced a DLT in the DLT observation period or. DLT evaluable patients will also include those who received all of their planned doses of PF-06863135 in the initial DLT observation period if Q2W dosing is being evaluated or at least all but one of their planned doses of PF-0686135 if Q1W dosing is being evaluated, provided a dose was not missed due to toxicity attributed to study drug. Safety information from any patients that do not meet DLT evaluable criteria could still be considered for overall dose escalation decisions although they would not factor into mTPI decision rules.

Any of the following adverse events observed within the DLT observation period considered related to PF-06863135 or PF-06863135 in combination with lenalidomide, pomalidomide, dexamethasone, will be classified as DLTs:

Hematological:

- Grade 4 neutropenia lasting >5 days. Except in lenalidomide combination cohort where it can be managed by dose reduction of lenalidomide in the next cycle.
- Febrile neutropenia (defined as an absolute neutrophil count [ANC] <1000/mm³ with a single temperature of >38.3°C [101°F], or a sustained temperature of ≥38°C [100.4°F] for more than one hour). If fever is determined to be a symptom of CRS confirmed by clinical course and cytokine levels and resolves in a manner consistent with CRS, this would no longer be considered a DLT, and the patient may resume treatment.
- Grade ≥3 neutropenia with infection.
- Grade 4 thrombocytopenia (unless the study entry baseline count was ≥25,000 and <50,000 to take into account bone marrow suppression due to multiple myeloma, in

PF-06863135

C1071001

Final Protocol Amendment 9, 28 March 2023

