5.4.2. SC Administration PF-06863135

Qualified and trained investigator site personnel will administer PF-06863135 to patients by SC injection. Ideally, each injection may be up to 2 mL in volume. However, if the maximum volume allowed per institution's policy is lower, the number of injections may increase to accommodate this difference in volume to ensure the correct final dose is delivered.

Study drug should be administered to the abdomen (with preference given to the lower quadrants when possible). Refer to [Appendix 9](#) for details on administration of multiple injections to the abdomen. Study staff should refer to the IP Manual for specific instructions on the handling and preparation of study drug.

Similar to IV dosing, during monotherapy dose escalation with Q1W SC PF-06863135 only each cycle will be 3 weeks in duration, and each patient will be treated 3 times during each cycle, unless dose delays or interruptions occur (see [Sections 5.5.1](#) and [5.5.2](#)). If patients are enrolled into Q2W SC dosing cohorts during dose escalation, each cycle will be 4 weeks in duration, and each patient will be treated twice during each cycle. On C1D1 for all patients, and on C0D1 for patients receiving a priming dose, PF-06863135 will be administered on an inpatient basis. On all other days, PF-06863135 will be administered on an outpatient basis).

PF-06863135

C1071001

Final Protocol Amendment 9, 28 March 2023

If patients are enrolled into Q2W SC dosing cohorts during dose escalation, each cycle will be 4 weeks in duration, and each patient will be treated twice during each cycle. On C1D1 for all patients, and on C0D1 for patients receiving a priming dose, PF06863135 will be administered on an inpatient basis. On all other days, PF06863135 will be administered on an outpatient basis.

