2. INTRODUCTION

This document describes the planned statistical analyses for Protocol C1071001 latest amendment, dated 06 Jun 2021. This SAP is meant to supplement the study protocol. This SAP supersedes the statistical considerations identified in the protocol and, where considerations are substantially different, they will be identified as such. Any deviations from this analysis plan will be described in the clinical study report (CSR). Any post-hoc, or unplanned analyses performed that are not specified in this SAP will be clearly identified in the CSR. This plan is developed and finalized prior to database lock of the clinical database. This SAP is written with consideration of the recommendations outlined in the International Conference on Harmonisation (ICH) E9 Guideline (Guidance for Industry: Statistical Principles for Clinical Trials) and on the ICH E3 Guideline (Guidance for Industry: Structure and Content of Clinical Study Reports).

Interim data may be analyzed and reported in an interim CSR at any timepoint (including at the primary completion date [PCD]) before the final ORR collection are complete. The following CSRs will contain any updated data collected after the interim CSR cutoff date.

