5. ANALYSIS SETS

Analysis Set	Description	Applicable Analysis (for additional information refer to section 6)
Full Analysis Set (FAS)	all enrolled participants.	Primary endpoint, main analysis (section 6.1.1.1)
DLT Evaluatable Set	patients that have experienced a DLT in the DLT observation period or received all of their planned doses of PF-06863135 in the initial DLT observation period if Q2W dosing is being evaluated or at least all but one of their planned doses of PF-0686135 if Q1W dosing is being evaluated, provided a dose was not missed due to toxicity attributed to study drug. Safety information from any patients that do not meet DLT evaluable criteria could still be considered for overall dose escalation decisions although they would not factor into mTPI decision rules.	DLT (see section 8.2.1)
Safety Analysis Set	all subjects who receive at least 1 full or partial dose of study medication.	DLT (see section 8.2.1) Safety (see Section 8.2.3) Demography and Baseline characteristics
PK Concentration Analysis Set	PF-06863135 PK Concentration Analysis Set is defined as all subjects randomized and treated who have at least 1 measurable PF-06863135 concentration.	PK Analysis (see Section 8.2.5.)
PK Parameter Analysis Set	PF-06863135 PK parameter analysis population is defined as all enrolled subjects treated who have sufficient information to estimate at least 1 of the PF-06863135 PK parameters of interest.	PK Analysis (see Section 8.2.5.)
PD/Biomarker Analysis Set	all enrolled subjects with at least 1 of the PD/Biomarkers evaluated at pre- and/or post-dose.	PD/Biomarker Endpoints (see Section 8.2.5.4)
Immunogenicity Analysis Set	PF-06863135 Immunogenicity analysis set: The immunogenicity analysis set is defined as patients who receive at least 1 dose of study treatment and have at least 1 ADA sample collected.	Immunogenicity Analysis(see Section 8.2.5.5.)
mITT Analysis Set (for evaluation of efficacy)	all subjects who have received at least one dose of study treatment. If the FAS is same as the mITT, the analysis should be run on FAS.	Efficacy Analysis (see Section 8.2.3)
Response Evaluatable Set	all patients who have received at least one dose of the study treatment, and has at least one post baseline efficacy assessment.	Efficacy Analysis (see Section 8.2.3)

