8.2. Statistical Analyses

8.2.1. Primary Analysis

The primary analysis will be based on the Safety Analysis Set. The analysis objective is to summarize the adverse event incidence and will implement Pfizer standard summaries for adverse events. The occurrence of DLTs observed in the dosing cohorts is used to estimate the MTD as described in the Study Design section. Adverse Events constituting DLTs will be listed per dose level. Because the intent is to find a desirable dose that meets the tolerability criteria based on DLT rate while demonstrating clinical activity based on response rate, descriptive statistics (n, frequency, and percentage) will be reported.

Corresponding listings of data will be generated. Adverse events and cytokine release syndrome will be summarized by dose cohorts and in aggregate.

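### SAP 6.2.1 gives two conflicting DLT-evaluability rules for unprimed Part 1, and the looser one can only lower the reported DLT rate

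*SAP*

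**What the plan says.** Protocol 3.2 makes a patient evaluable if a DLT occurred in the observation period. Otherwise the patient needs every planned dose under Q2W dosing, or "at least all but one of their planned doses of PF-0686135 if Q1W dosing is being evaluated". In either case no dose may have been missed because of toxicity attributed to study drug. The DLT Evaluable Set in SAP Section 5 repeats this, and so does the first paragraph of SAP 6.2.1. Section 5 adds that safety information from other patients may inform escalation, "although they would not factor into mTPI decision rules".

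SAP 6.2.1 then introduces a list of criteria to be used in judging adequate dosing. The entry for unprimed cohorts is "Part 1 (no priming): At least 1 dose of the PF-06863135". The entries for the other parts use a 75% threshold.

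On the denominator, the analysis-set table in SAP Section 5 lists DLT against both the DLT Evaluable Set and the Safety Analysis Set. SAP 8.2.1 states: "The primary analysis will be based on the Safety Analysis Set". SAP 8.2.3 allows the DLT Evaluable Set where applicable. Protocol 9.2.2 bases the MTD on DLT-evaluable patients, which it equates with the per-protocol set of 9.1.

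SAP Section 2 promises: "This SAP supersedes the statistical considerations identified in the protocol and, where considerations are substantially different, they will be identified as such". The one-dose rule is not identified as a difference.

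**The concern.** A programmer cannot satisfy both texts of 6.2.1. A patient who took one of three weekly doses and had no DLT is outside the set under the paragraph and inside it under the bullet. The bullet also lacks the toxicity proviso. Someone who stopped after the first dose for a drug toxicity short of a DLT would therefore count as a DLT-free evaluable patient.

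DLT is the Part 1 primary endpoint, and SAP 8.2.1 promises counts and percentages. If neither the rule nor the denominator is fixed, the same data can give two different DLT rates at a dose level. The choice between them would be made at the programming stage and not in the plan.

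**Working it through.** **1. The plan's own table.** SAP Table 1 and protocol Table 4 are the same mTPI table. The inputs, from protocol 9.2.1, are a Beta(0.5, 0.5) prior, a target of 0.25, an interval of 0.20 to 0.30 and an exclusion threshold of 0.95. With posterior Beta(0.5 + x, 0.5 + n − x), the decision is the largest of:
- P(p < 0.20)/0.20, escalate;
- P(0.20 < p < 0.30)/0.10, stay;
- P(p > 0.30)/0.70, de-escalate, shown as unacceptable when P(p > 0.25) > 0.95.

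All 67 filled cells are reproduced. The table is sound, and the question is only who counts in n.

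**2. Doses required of a patient without a DLT.** Protocol 5.4.2 says of weekly unprimed dosing that "each cycle will be 3 weeks in duration, and each patient will be treated 3 times during each cycle". For Q2W it plans two doses in a four-week cycle.

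| Schedule, unprimed | Paragraph, Section 5, protocol 3.2 | Bullet |
|---|---|---|
| Q1W, 3 planned | 3 − 1 = 2 of 3 (66.7%) | 1 of 3 (33.3%) |
| Q2W, 2 planned | 2 of 2 | 1 of 2 |

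**3. The other bullets, counting full doses.** Part 1.1 weekly is 0.75 × 4 = 3 of 4, which is all but one. Part 1.1 Q2W is 0.75 × 2 = 1.5, so 2 of 2. Both agree with the paragraph on maintenance doses, so among the monotherapy bullets only the unprimed one has a looser dose count. The bullets for Parts 1C, 1D and 1E also require 75% of the combination drug. That is 0.75 × 21 = 15.75, or 16 of 21 daily doses, of lenalidomide or pomalidomide, and 0.75 × 4 = 3 of 4 doses of dexamethasone. Neither protocol 3.2 nor SAP Section 5 contains this condition. It works the other way, because it can remove DLT-free patients.

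**4. Direction.** A patient with a DLT is evaluable under either text. The bullet can therefore add only patients with no DLT. The rate x/n becomes x/(n + 1), a relative fall of 1/(n + 1): 1/7 = 14.3% at n = 6, 1/10 = 10.0% at n = 9 and 1/16 = 6.3% at n = 15. In the mTPI table, one such addition changes ten decisions, all to a less restrictive one (for example, stay at 1/4 becomes escalate at 1/5).

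**5. The 30% cap.** Protocol 3.3 bars a dose with a DLT incidence above 30% from being the MTD and gives 3 of 9 as an example. Over the 6 to 16 patients of protocol 9.2.2, one added patient satisfies x/n > 0.30 and x/(n + 1) ≤ 0.30 in exactly three cases:
- 2/6 = 33.3% to 2/7 = 28.6%;
- 3/9 = 33.3% to 3/10 = 30.0%;
- 4/13 = 30.8% to 4/14 = 28.6%.

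The third case needs the protocol's upper figure of 16, because SAP 4.2 stops at 12.

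**6. Scope.** Protocol 1.2.3.1 reports "23 in Part 1 IV dose escalation, 30 in Part 1 SC dose escalation, 20 in Part 1.1 SC priming dose cohorts". The bullet governs 23 + 30 = 53 of 101 enrolled patients (52.5%). That is how many patients the rule applies to, not how many it reclassifies.

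**The case against.** The strongest reply is that little can move. The endpoint is defined as the number of DLTs, and that count and the per-level listing are the same under every set. Enrollment is complete. The RP2D was chosen on safety, efficacy, PK and pharmacodynamic data (protocol 3.4). If no MTD is reached, the MAD is simply the highest dose evaluated (protocol 3.3). The number of under-dosed DLT-free patients could be zero. All of this stands, and it limits the point to the reported rate and a possible borderline MTD call.

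A second reply is that the bullet follows the protocol 9.1 per-protocol set, which also starts from at least one dose. That set additionally excludes major treatment deviations in the observation period, so it does not rescue a bare one-dose rule. It does show that the protocol carries two tests of evaluability, and the remedy has to deal with both.

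A third reply is that the bullet is only a minimum precondition on top of the paragraph. The lead-in presents the list as the test of adequate dosing, and the Part 1.1 bullets match the paragraph's dose count. That reading is therefore not supported.

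**Conclusion.** The contradiction is real and lies within one SAP section. For unprimed Part 1, the paragraph needs 2 of 3 weekly or 2 of 2 two-weekly doses, while the bullet accepts one. Following the bullet can only lower the reported DLT rate, by a relative 6.3% to 14.3% per added patient at the sizes shown. In three borderline configurations it crosses the 30% cap. The documents give neither DLT nor under-dosing counts by level, so the effect is possible and not shown.

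Several stronger readings are tempting but unsupported:
- **The Safety Analysis Set could move the MTD.** Protocol 9.2.2 and SAP Section 5 tie the MTD and mTPI to evaluable patients. Only the denominator of the reported percentages is unclear.
- **Past escalation or the RP2D is in doubt.** Nothing in the documents shows that the bullet was used in escalation, and the RP2D is already selected.
- **The 53 patients measure the effect.** They are scope only.
- **SAP 2.1 shortens the DLT window.** Its 21- and 28-day wording is design narrative. The same section also says end of Cycle 1, and 6.2.1 adds Cycle 0 for primed patients.

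**What to change.** 1. In SAP 6.2.1, replace the unprimed Part 1 bullet with the protocol 3.2 / SAP Section 5 rule. A patient is evaluable with a DLT, with all planned Q2W doses, or with all but one planned Q1W dose, and in the dosing cases no dose may have been missed for drug toxicity.
2. In SAP Section 5, 8.2.1 and 8.2.3, name the DLT Evaluable Set as the denominator for DLT rates and the MTD. Keep the Safety Analysis Set for AE summaries and DLT listings.
3. Reconcile that set with the per-protocol set in protocol 9.1 and 9.2.2. Identify the added 75% combination-drug condition for Parts 1C, 1D and 1E as a departure from the protocol.
4. If the one-dose rule was intended, identify it as a departure, as SAP Section 2 promises, and report DLT rates under both rules.
5. As housekeeping, align the SAP 2.1 wording with the end of Cycle 1, including Cycle 0 where a priming dose is given.

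The cost is mainly SAP wording, with no new data. SAP 5.2 already foresees an update before database lock. It should not be assumed that no protocol change is needed. The opening of protocol Section 9 sends major modifications of the primary endpoint definitions or their analyses to an amendment, and the sponsor should check whether item 3 falls under that. The downside is that a few unprimed patients may leave the denominator, so reported DLT rates may rise slightly.

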5.5. Recommended Dose Modifications

Every effort should be made to administer investigational product on the planned dose and schedule.

PF-06863135

C1071001

Final Protocol Amendment 9, 28 March 2023

In the event of significant toxicity, dosing may be delayed and/or reduced as described below. In the event of multiple toxicities, dose modification should be based on the worst toxicity observed. Patients are to be instructed to notify investigators at the first occurrence of any adverse symptom.

Dose modifications of PF-06863135, lenalidomide, pomalidomide and dexamethasone, may occur in one of three ways:

- Within a cycle: dosing interruption until adequate recovery and dose reduction, if required, during a given treatment cycle;
- Between cycles: next cycle administration may be delayed due to persisting toxicity when a new cycle is due to start;
- In the next cycle: dose reduction may be required in a subsequent cycle based on toxicity experienced in the previous cycle.

In Parts 1E and 2E, if a dose of PF-06863135 is delayed or interrupted, then dexamethasone should not be administered until PF-06863135 administration is restarted.

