5.5.2. Dose Delays

Re-treatment following treatment interruption for treatment-related toxicity or at the start of any new cycle should not occur until all of the following parameters have been met:

- ANC $\geq 1,000/\text{mm}^3$ for PF-06863135, dexamethasone, and lenalidomide; $\geq 500/\text{mm}^3$ for pomalidomide;
- Platelets count $\geq 25,000/\text{mm}^3$ for PF-06863135 and dexamethasone; $\geq 30,000/\text{mm}^3$ for lenalidomide; $\geq 50,000/\text{mm}^3$ for pomalidomide;
- Non-hematologic toxicities have returned to baseline or Grade ≤ 1 severity (or, at the investigator's discretion, Grade ≤ 2 if not considered a safety risk for the patient).
- Recovery of treatment-emergent peripheral neuropathy to Grade ≤ 1 severity.

If a treatment delay results from worsening of hematologic or biochemical parameters, the frequency of relevant blood tests should be increased as clinically indicated.

If these conditions are met within 3 weeks of treatment interruption or cycle delay, study treatment may be resumed. Refer to the Dose Reductions Section 5.5.3 for adverse events requiring dose reduction at the time of treatment resumption.

If these conditions are not met, treatment resumption must be delayed up to a maximum of 3 weeks. If patients require discontinuation of study treatment for more than 42 days of Day 1 of the current cycle, then study treatment should be permanently discontinued, unless the investigator's benefit/risk assessment suggests otherwise after discussion with the Sponsor's medical monitor.

If a treatment interruption continues beyond the last day of the current cycle, then the day when treatment is restarted will be counted as Day 1 of the next cycle.

Recommended guidelines for dose delays of PF-06863135 for participants who have active [confirmed (positive by regulatory authority-approved test) or presumed (test pending/clinical suspicion)] SARS-CoV2 infection can be found in [Appendix 10](#).

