8.2.3.5. Treatment Administration/Compliance

Listings and tables by dose level will be provided. Day 1 of a cycle is the date of first dose within that cycle. Each cycle is a 3-week period for Part 1, or 4-week period for Parts 1.1 1C, 1D, 1E, 2A, 2C, 2D, or 2E except cycle 0 for priming dose. The safety analysis set will be used.

The following will be summarized by subject for each dose level:

- Number of subjects per dose level;
- Median and range of number of cycles started per subject;
- Number (%) of subjects starting a cycle (1, 2, 3...);
- Number (%) of subjects with cycle delays;
- Number (%) of dose interruptions (include both known and unknown dates);
- Number (%) of subjects with dose reductions;
- Number (%) of each reason (AE vs. Other) for cycle delays, dose interruptions and dose reductions;
- Time on treatment (median, range).

The following will be summarized by cycle received for each dose level:

- Total number of cycles started;
- Number of cycles started per subject (median, range);

The following will be summarized for cumulative dose by dose level and cycle: Summary statistics (mean, median, standard deviation and range) of cumulative dose and percent of starting dose (compared to Day 1 dose of each cycle).

Listings by subject (ordered by dose level): start date and stop date of each dosing period within each cycle (including records with 0 mg), administered total daily dose for each period, any missed doses with unknown dates (Y/N), number of missed doses with unknown dates, reason for any dosing changes. Listings by subject and each cycle (ordered by dose level): cycle length, total planned dose, administered total dose, percentage of planned dose, dose delay (yes/no), dose reduction (yes/no), and dose interruption (yes/no).

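### For a completed cycle, the SAP's relative dose intensity leaves out cycle duration, so it overstates intensity when a delay before the next cycle lengthens it

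*SAP*

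**What the plan says.** SAP 6.2.1 introduces the measure with "Relative dose intensity at each cycle will be calculated as follows" and then goes through the Parts. For each Part listed it says "Cycle length is determined as entered by the site", takes the sum of doses administered in that cycle, and gives a planned dose. For Part 1 without priming: "The total planned dose will be the (assigned dose of PF-06863135 *3". For Part 1.1 weekly and Part 2A: "The total planned dose = (maintenance dose of PF-06863135 * 4". The multiplier is 2 for Part 1.1 every two weeks, and 21 for lenalidomide and pomalidomide. No division is written out.

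Time changes the planned dose in one situation only, discontinuation before the end of a cycle. The SAP's example for Part 1 is "if patient discontinues after CXD2, the planned dose will be (assigned dose of PF-06863135 *1".

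SAP 8.2.3.5 gives the planned lengths: "Each cycle is a 3-week period for Part 1, or 4-week period for Parts" other than Part 1 (Cycle 0 excepted). It also dates Day 1 of a cycle by the first dose given in it.

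Protocol 5.5 names between-cycle delay as one of three kinds of dose modification: "next cycle administration may be delayed due to persisting toxicity when a new cycle is due to start". Protocol 5.5.2 limits the delay to 3 weeks and says that, when an interruption runs past the last day of a cycle, "the day when treatment is restarted will be counted as Day 1 of the next cycle". Protocol 5.5.1 says that doses omitted for toxicity are not made up within the cycle.

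**The concern.** Dose intensity is a rate. Relative dose intensity should compare dose per unit time as delivered with dose per unit time as planned. In the SAP the planned dose for a completed cycle is fixed and the cycle's actual length enters neither numerator nor denominator. Because Day 1 of the next cycle is the day dosing resumes, time lost to a delay is added to the earlier cycle. That cycle becomes longer while its ratio stays the same.

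The treatment of time is also one-sided: a cycle cut short by discontinuation has its planned dose reduced, but a cycle that runs long has no adjustment.

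At stake is the accuracy of a descriptive tolerability measure. A reader who takes the figure as an intensity would read a cycle that took 35 days in place of 28 as delivered in full.

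**Working it through.** The documents state no value of relative dose intensity to reproduce. The SAP's one worked example can be checked: with Part 1 doses on Days 1, 8 and 15, one dose is due by Day 2, so the planned dose is the assigned dose × 1, as the SAP says.

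**Inputs**
- Planned doses per cycle: 3 (Part 1), 4 (weekly, other Parts listed), 2 (Part 1.1 every two weeks); SAP 6.2.1.
- Planned cycle length: 21 days (Part 1) or 28 days (other Parts); SAP 8.2.3.5.
- Delay before the next cycle: 7, 14 or 21 days. These are illustrative values within the 3-week maximum of Protocol 5.5.2.

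**Formulas**
- SAP ratio = administered dose / planned dose.
- Time-adjusted ratio = (administered dose / actual cycle days) / (planned dose / planned cycle days) = SAP ratio × planned days / actual days.

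**Case 1: all planned doses given, next cycle late.** The SAP ratio is 100% throughout.

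| Delay | 28-day cycle, time-adjusted | 21-day cycle, time-adjusted |
|---|---|---|
| 7 days | 28/35 = 80.0% | 21/28 = 75.0% |
| 14 days | 28/42 = 66.7% | 21/35 = 60.0% |
| 21 days | 28/49 = 57.1% | 21/42 = 50.0% |

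The 28-day column is the same for weekly and two-weekly dosing, and for 21 daily doses of lenalidomide or pomalidomide, because only the ratio of days matters.

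**Case 2: one dose omitted, cycle not lengthened.** Planned and actual days are equal, so the two ratios agree: 2/3 = 66.7%, 3/4 = 75.0%, 1/2 = 50.0%. There is no overstatement.

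**Case 3: one dose omitted and the cycle 7 days longer.**
- Three planned doses: SAP 66.7%; time-adjusted (2/28)/(3/21) = 50.0%.
- Four planned doses: SAP 75.0%; time-adjusted (3/35)/(4/28) = 60.0%.
- Two planned doses: SAP 50.0%; time-adjusted (1/35)/(2/28) = 40.0%.

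The overstatement is therefore the factor actual days / planned days, and it arises only where the cycle is lengthened.

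**The case against.** The strongest reply is that the SAP lists ingredients and does not write the division, so cycle length might be meant to enter. This has some force: its role is unstated. But the section claims to say how the measure is calculated, and the only planned quantity it gives for a completed cycle is a dose. A programmer who follows it obtains administered over planned dose.

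A second reply is that delays are visible elsewhere. SAP 8.2.3.5 tabulates subjects with cycle delays, interruptions and reductions, with reasons, and lists cycle length beside percentage of planned dose. It does not list relative dose intensity among its summaries. This stands as a limit on the harm. However, the tables count delays without giving their length, which appears only in a by-subject listing.

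A third reply is that the Day 1 restart rule in Protocol 5.5.2 concerns interruptions running past the end of a cycle, where doses have often been missed and the ratio has already fallen. That is true of that sentence. Protocol 5.5 separately provides for a pure between-cycle delay, and SAP 8.2.3.5 dates each cycle from its first dose, so Case 1 can occur.

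Four stronger readings are tempting, and the documents do not support them:
- That time plays no part at all. Planned dose is prorated at discontinuation.
- That any patient with a delay scores 100%. Case 1 requires every planned dose of the cycle to have been given; toxicity omissions lower the ratio.
- That the neutropenia frequency in Protocol 1.2.3.1 (78.0% of 41 patients) shows how often this happens. It is an all-causality adverse event frequency with no grade attached, not a delay rate.
- That dose finding is distorted. DLT evaluability in SAP 6.2.1 has its own criteria: a fixed 28 days from C1D1 in the priming and combination Parts, and at least one dose in Part 1. Nothing links relative dose intensity to the mTPI rules or the MTD. The SAP also plans no comparisons between dose groups (6.5).

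**Conclusion.** The point holds in a limited form. For a completed cycle, the calculation in SAP 6.2.1 gives percentage of planned dose under the name of an intensity, and overstates intensity by the ratio of actual to planned cycle days. In the fully dosed case, 100% would be reported against 57.1% to 80.0% (28-day cycle) or 50.0% to 75.0% (21-day cycle) for delays of 21 down to 7 days.

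These figures assume that the listed ingredients are simply divided and that the delay is booked to the earlier cycle. The 57.1% figure also uses the full 3-week delay after a 28-day cycle. Protocol 5.5.2 has a separate 42-day limit counted from Day 1 of the current cycle. If that limit ends the cycle first, the lowest value for a 28-day cycle is 28/42 = 66.7%; the 21-day figure stays at 21/42 = 50.0%. The average overstatement cannot be computed, because no delay frequency is given. The consequence is confined to descriptive exposure reporting.

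**What to change.** In SAP 6.2.1, write out the formula: relative dose intensity = (administered dose / actual cycle days) / (planned dose / planned cycle days). Count actual duration from Day 1 to Day 1 of the next cycle, and take planned duration as 21 or 28 days according to Part. Keep the existing proration for a final cycle that ends in discontinuation, where there is no next Day 1. Retain the present ratio as percentage of planned dose, to match SAP 8.2.3.5, and report both. At the least, rename the present ratio.

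The cost is one formula and its programming. Dosing dates and cycle length are already collected, so no new data are needed. The downside is that reported intensities will be lower wherever cycles were lengthened.
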